6.2. Exclusion Criteria

Patients will be excluded from study enrollment if they meet any of the following criteria at screening:

Medical Conditions

- [10] Have type 1 diabetes mellitus (T1DM)
- [11] Had chronic or acute pancreatitis any time prior to study entry (Visit 1)
- [12] Have a history of proliferative diabetic retinopathy or diabetic maculopathy (a dilated fundoscopic exam, performed by an ophthalmologist or optometrist between Visit 2 and Visit 3, is required to confirm eligibility) or nonproliferative diabetic retinopathy that requires acute treatment
- [13] Have a history of ketoacidosis or hyperosmolar state/coma
- [14] Have had 1 or more episode of severe hypoglycemia and/or 1 or more episode of hypoglycemia unawareness within the 6 months prior to Visit 1

- [15] Have a known clinically significant gastric emptying abnormality (for example, severe diabetic gastroparesis or gastric outlet obstruction), have undergone gastric bypass (bariatric) surgery or restrictive bariatric surgery (for example, Lap-Band[®]), or chronically take drugs that directly affect GI motility
- [16] New York Heart Association Functional Classification IV congestive heart failure
- [17] Have any of the following CV conditions within 2 months prior to Visit 1: acute myocardial infarction, cerebrovascular accident (stroke), or hospitalization for CHF
- [18] Have acute or chronic hepatitis, signs or symptoms of any other liver disease, or an alanine aminotransferase (ALT) level >3.0 the upper limit of normal (ULN) for the reference range, as determined by the central laboratory. Patients with nonalcoholic fatty liver disease are eligible to participate only if their ALT level is ≤3.0 the ULN for the reference range
- [19] Have evidence of a significant, uncontrolled endocrine abnormality (for example, thyrotoxicosis or adrenal crises), in the opinion of the investigator
- [20] Have family or personal history of medullary thyroid carcinoma or Multiple Endocrine Neoplasia syndrome type 2
- [21] Have a serum calcitonin level of
 - (a) ≥20 ng/L at Visit 1, if eGFR ≥60 mL/min/1.73m²
 - (b) ≥35 ng/L at Visit 1, if eGFR <60 mL/min/1.73m²
- [22] Have evidence of significant, active autoimmune abnormality (for example, lupus, rheumatoid arthritis) that, in the opinion of the investigator, is likely to require concurrent treatment with systemic glucocorticoids in the next 12 months.
- [23] Known or suspected hypersensitivity to trial product(s) or related products
- [24] History of hypersensitivity to insulin glargine
- [25] Have had a transplanted organ (corneal transplants [keratoplasty] allowed) or awaiting an organ transplant
- [26] Have a history of an active or untreated malignancy or are in remission from a clinically significant malignancy (other than basal or squamous cell skin cancer, in situ carcinomas of the cervix, or in situ prostate cancer) for less than 5 years
- [27] Have a history of any other condition (such as known drug, alcohol abuse, or psychiatric disorder) that, in the opinion of the investigator, may preclude the patient from following and completing the protocol
- [28] Have any hematological condition that may interfere with HbA1c measurement (for example, hemolytic anemias, sickle cell disease)

Prior/Concomitant Therapy

- [29] Have a history of insulin therapy except for the use of insulin for treatment of gestational diabetes or acute, temporary use of insulin (≤ 14 days), for example, for acute illness, hospitalization, elective surgery
- [30] Treatment with any glucose-lowering agent(s) other than stated in the inclusion criteria (including DPP-4 inhibitors and GLP-1 receptor agonists) in a period of 3 months before screening prior to Visit 1
- [31] Are receiving chronic (>2 weeks or 14 days) systemic glucocorticoid therapy (excluding topical, intra-ocular, intranasal, or inhaled preparations) or have received such therapy within 1 month of Visit 1
- [32] Have been treated with drugs that promote weight loss (for example, Saxenda [liraglutide 3.0 mg], Xenical[®] [orlistat], Meridia[®] [sibutramine], Acutrim[®] [phenylpropanolamine], Sanorex[®] [mazindol], Apidex[®] [phentermine], BELVIQ[®] [lorcaserin], Qsymia[™] [phentermine/topiramate combination], Contrave[®] [naltrexone/bupropion], or similar other body weight loss medications including over-the-counter [OTC] medications [for example, alli[®]]) within 3 months prior to Visit 1 and/or between study entry (Visit 1) and randomization (Visit 3)

Prior/Concurrent Clinical Trial Experience

- [33] Are currently enrolled in any other clinical study involving an investigational product or any other type of medical research judged not to be scientifically or medically compatible with this study
- [34] Have participated, within the last 30 days, in a clinical study involving an investigational product. If the previous investigational product has a long half-life, 5 half-lives or 30 days (whichever is longer) should have passed
- [35] Have previously completed or withdrawn from this study or any other study investigating LY3298176

Other Exclusions

- [36] Are investigator site personnel directly affiliated with this study and/or their immediate families. Immediate family is defined as a spouse, parent, child, or sibling, whether biological or legally adopted
- [37] Are Lilly employees
- [38] Are unwilling or unable to comply with completing a diary to record data from the subject

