Unless specified otherwise, safety assessments will be based on all available data, irrespective of whether they were obtained after the participants had discontinued the study drug or whether the participant had been given rescue medication. Summary statistics will be provided for incidence of TEAEs, serious adverse events, and study discontinuation due to AEs or death during the treatment period. Counts and proportions of subjects experiencing AEs will be reported for each treatment group, and Fisher’s exact test will be used to compare the treatment groups. For continuous laboratory analytes, summary statistics will be provided by visit, with statistical comparisons among treatment at each visit conducted using an MMRM analysis. Selected safety analysis (for example, hypoglycemia) will be conducted after excluding data while on rescue therapy. Additional details, including analysis of AEs of special interest, will be provided in the SAP.

2. Schedule of Activities

The Schedule of Activities described below should be followed for all patients enrolled in Study GPGM. However, for those patients whose participation in this study is affected by severe acute respiratory syndrome coronavirus 2 (SARS-CoV-2), the virus that causes the novel Coronavirus Disease 2019 (COVID-19), please refer to [Appendix 8](#) for additional instructions.

Table GPGM.1. Schedule of Activities

	Study Period I		Study Period II 52 Weeks																								Study Period III Variable				Study Period IV				
	Screening Lead in		Treatment Period																								Safety F/U								
Visit	1	2	3 ^a	4	5	6	7	8	9	10	11	12	13	14	15	16	17	18	19	20	21	22	23	24	25	26	27	28	29	FT V ^z	ET ^b	801			
Week of Treatment	-3	-2	0	1	2	3	4	5	6	7	8	10	12	15	16	20	23	24	28	32	35	36	42	52	62	72	78	88	104			4 week post end of tx			
Allowable Deviation (days) ^c	-	±3	±7	±3	±3	±3	±3	±3	±3	±3	±3	±3	±3	±3	±3	±3	-	±3	±3	±3	-	±3	±7	±7	±7	±7	±7	±7	±7			±3			
Fasting Visit ^d			X		X		X				X		X		X	X		X					X	X			X		X	X	X	X			
PK only Visit																	X				X														
Telephone Visit						X		X	X			X																							
Informed consent	X																																		
Randomization			X																																
Clinical Assessments																																			
Medical history ^e	X																																		
Physical	X																								X							X			
Height	X																							X											
Weight ^f	X		X				X				X		X		X	X		X				X	X	X	X	X	X	X	X	X	X	X	X	X	

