- d) Age ≥ 50 years, history of CKD, and an estimated glomerular filtration rate < 60 mL/min/1.73m² (CKD-Epidemiology[CKD-EPI]) on consecutive measurements (Visit 1 and Visit 2)

OR

- e) Age ≥ 50 years and congestive heart failure (CHF) documented as a history of CHF by the New York Heart Association Functional Classification II to III

[5] Are of stable weight ($\pm 5\%$) ≥ 3 months prior to Visit 1 and agree to not initiate an intensive diet and/or exercise program during the study with the intent of reducing body weight other than the lifestyle and dietary measures for diabetes treatment

[6] Have a BMI ≥ 25 kg/m² at Visit 1

[7] Eighteen years or older at the time of signing informed consent

Male patients:

Male patients should be willing to use reliable contraceptive methods throughout the study and for at least 3 months after last injection

Female patients:

Female patients not of childbearing potential due to surgical sterilization (hysterectomy, bilateral oophorectomy, or tubal ligation) or menopause.

Women with an intact uterus are deemed postmenopausal if they are 45 years old, and

- have not taken hormones or oral contraceptives within the last year and had cessation of menses for at least 1 year

OR

- have had at least 6 months of amenorrhea with follicle-stimulating hormone (FSH) and estradiol levels consistent with a postmenopausal state (FSH ≥ 40 mIU/mL and estradiol < 30 pg/mL).

Female patients of childbearing potential (not surgically sterilized and between menarche and 1-year postmenopausal) must

- test negative for pregnancy at Visit 1 based on a serum pregnancy test

AND

- if sexually active, agree to use 2 forms of effective contraception, where at least 1 form is highly effective for the duration of the trial and for 30 days thereafter
- not be breastfeeding

[8] In the investigator's opinion, are well motivated, capable, and willing to

- perform SMBG (up to 7 measures in a day)
- learn how to self-inject treatment (LY3298176 or insulin glargine), as required for this protocol (visually impaired persons who are not able to perform the injections must have the assistance of a sighted individual trained to inject the study drug; persons with physical limitations who are not able to perform the injections must have the assistance of an individual trained to inject the study drug)
- are willing and able to inject study drug QW/once daily
- maintain a study diary, as required for this protocol

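### Exclusions [11], [14] and [17] stop at Visit 1, so pancreatitis, severe hypoglycemia, MI, stroke or CHF hospitalization between Visit 1 and randomisation at Visit 3 does not exclude a patient as written

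*Protocol*

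**What the plan says.** Protocol 6.2 opens with "Patients will be excluded from study enrollment if they meet any of the following criteria at screening". Three of its criteria look back from Visit 1:

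- [11]: "Had chronic or acute pancreatitis any time prior to study entry (Visit 1").
- [14]: severe hypoglycemia and/or "1 or more episode of hypoglycemia unawareness within the 6 months prior to Visit 1".
- [17]: "Have any of the following CV conditions within 2 months prior to Visit 1: acute myocardial infarction, cerebrovascular accident (stroke), or hospitalization for CHF".

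Exclusion [32], on weight-loss drugs, has a different end-point: "within 3 months prior to Visit 1 and/or between study entry (Visit 1) and randomization (Visit 3").

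The Schedule of Activities puts Visits 1, 2 and 3 at Weeks -3, -2 and 0, with ±7 days allowed at Visit 3. Under Protocol 5.1, eligibility is established at Visit 2 from the screening laboratory results, a fundoscopic exam follows between Visits 2 and 3, and randomisation and the first LY3298176 dose take place at Visit 3. SAP 4.1 names retinopathy status as the one item left open at Visit 2. Protocol 7.2 randomises patients who meet all enrollment criteria, and Section 6 bars waivers.

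**The concern.** The interval from Visit 1 to Visit 3 covers screening plus lead-in (the lead-in proper is Visit 2 to Visit 3). It falls after the three windows close and before study drug starts. A patient with an acute MI one week before Visit 3 has had no MI in the 2 months before Visit 1, so [17] does not apply. The same holds for a severe hypoglycemic episode under [14] and for pancreatitis under [11].

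The stake is patient safety and uniform decisions across sites. The population is selected for high cardiovascular risk and may be taking a sulfonylurea. Two sites facing the same event could decide differently and both be within the protocol.

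Pancreatitis raises a further problem. Criterion [11] admits a patient whose pancreatitis fell between Visits 1 and 3, while 8.1.1 says study drug is to be discontinued for acute or chronic pancreatitis. Unlike the medullary thyroid carcinoma and malignancy items in the same list, the pancreatitis item is not limited to events after randomisation.

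**Working it through.** **Step 1. Does any other text close the interval?**

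| Text | Does it cover [11], [14], [17] events from Visit 1 to Visit 3? |
|---|---|
| Protocol 5.1 and SAP 4.1 | No. Eligibility is settled at Visit 2; the later check named is the eye exam. |
| Schedule of Activities | Medical history is taken at Visit 1 only. Adverse events are collected from Visit 2 and hypoglycemia is reviewed at Visit 3, so sites would see such events, but no rule tells them what follows. |
| Protocol 9.2 | Treats procedures before Visit 3 as screening. That may stretch the 6.2 lead sentence, but not a window that names Visit 1 as its end. |
| Exclusion [27] | Permits exclusion on the investigator's opinion that a condition may prevent the patient from following and completing the protocol; it does not require it. |
| Protocol 7.2 | Refers back to the criteria as written. |
| Protocol 8.1.3 (inadvertent enrollment) and the matching EAS/FAS exclusion in SAP 5.1 | No. 8.1.3 concerns patients who failed the criteria; these patients met them. |

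Exclusion [32] shows that the drafters had wording for this interval. If windows ending at Visit 1 already ran on to Visit 3, [32]'s second clause would be redundant.

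**Step 2. Length of the interval.** Visit 1 (Week -3) to Visit 3 (Week 0) is 21 days; adding the +7-day allowance gives 28. The lead-in alone is 14 days.

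**Step 3. Reproduce the plan's event figure.** Protocol 10.1 expects 110 patients with MACE-4 from 1878 patients at 33 to 40 per 1000 patient-years, with 2% exposure lost and 18 to 22 months of follow-up.

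Events = N × 0.98 × (months/12) × rate

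- 1878 × 0.98 × (18/12) × 0.040 = 110.4
- 1878 × 0.98 × (22/12) × 0.033 = 111.3

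Both agree with 110, pairing the higher rate with the shorter follow-up and the lower rate with the longer.

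**Step 4. Apply the same rate to the uncovered interval.**

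Patients = 1878 × (days/365.25) × rate

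| Days | At 33 per 1000 PY | At 40 per 1000 PY |
|---|---|---|
| 14 (lead-in only) | 2.4 | 2.9 |
| 21 (nominal Visit 1 to Visit 3) | 3.6 | 4.3 |
| 28 (with +7 days) | 4.8 | 5.8 |

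MACE-4 also counts CV death and hospitalization for unstable angina, neither of which is in [17]. The figures are therefore an upper guide for MI plus stroke. The documents give no rate for CHF hospitalization, severe hypoglycemia or pancreatitis, so those parts cannot be sized.

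**The case against.** The strongest reply is that these events would not go unseen and nothing compels randomisation. Adverse events are collected at Visits 2 and 3, hypoglycemia recording starts at Visit 2 (9.2.2.1), and baseline assessments must be complete before IWRS processing. A site could reasonably read the screening language in 9.2 as covering the whole run-up to Visit 3, or use [27] for an MI or stroke days earlier. This stands in part: randomisation after such an event would often be prevented in practice. But it relies on judgement where the criteria are meant to give a rule.

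A reader might infer that [32] is the only criterion reaching past Visit 1. It is not. Exclusion [12] is confirmed by the exam between Visits 2 and 3, inclusion [4]d needs an eGFR at Visit 2, and exclusions [13], [16] and [26] carry no Visit 1 cut-off. The gap is confined to the three criteria named.

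A reader might also extend the point to pregnancy, since inclusion [7] asks for a negative serum test at Visit 1. Schedule footnote q already requires a Visit 3 urine result before randomisation and first injection, so there is no gap there.

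**Conclusion.** The point holds for [11], [14] and [17]. Followed as written, they leave a nominal 21 days before randomisation uncovered, and [11] and 8.1.1 do not agree. The size is at most about 4 patients for MI plus stroke at the nominal interval, or about 6 at 28 days. This assumes that the protocol's on-study MACE-4 rate applies before randomisation and that 1878 patients pass through the interval.

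Two stronger readings are not supported. First, 3.6 to 4.3 is not the number of patients wrongly randomised. It includes deaths and unstable angina, and a patient affected by the gap must also survive, attend Visit 3 and be taken forward by the investigator; the documents give no basis for estimating that. Second, a reader might infer that early complications of an event before randomisation would pull the MACE-4 hazard ratio toward 1. Only later events in these few patients could enter the analysis, against about 110 planned. No recurrence rate is given, and the trial enrols patients with prior MI and stroke by design.

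The primary HbA1c analysis is not affected, and no sample size, power or alpha figure changes.

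**What to change.** - Reconcile the end-points of [11], [14] and [17] with the interval wording that [32] already uses, running from study entry to randomisation. Leave the existing look-back lengths unchanged; no new clinical window is needed.
- Reconcile [11] with the pancreatitis item in 8.1.1, so that the text on entry and the text on stopping study drug agree.
- Add a confirmation of eligibility at Visit 3, before the IWRS call, using the adverse event and hypoglycemia information already collected there.

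The cost is a wording change in 6.2, with 8.1.1 checked against it, and one confirmation step. No new procedure or sample is required. The downside is a few more screen failures, who cannot be rescreened under 6.4.

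If enrollment has already closed, the sponsor can instead identify randomised patients who had one of these events between Visits 1 and 3. The listing of adverse events before first dose in SAP 5.13.1 is a starting point, supplemented by medical history because 9.2 allows findings before Visit 3 to be recorded there.

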6.3. Lifestyle Restrictions

Per the Schedule of Activities (Section 2), qualified medical staff will provide diabetes management counseling, which will include instructions on diet and exercise and education about the signs, symptoms, and treatment of hypoglycemia, should it occur.

Patients should continue their usual exercise habits and generally follow a healthy meal plan (with consistent meal size and time of day) throughout the course of the study. Dietary counseling may be reviewed throughout the study, as needed. Per inclusion criterion [5] (Section 6.1), patients should not initiate during the study an organized diet and/or exercise weight reduction program other than the lifestyle and dietary measures for diabetes treatment.

Study participants should be instructed not to donate blood or blood products during the study.

6.4. Screen Failures

Individuals who do not meet the criteria for participation in this study (screen failure) must not be rescreened.

7. Treatments

7.1. Treatments Administered

Patients will be randomized in a 1:1:1:3 ratio to receive LY3298176 5 mg, LY3298176 10 mg, LY3298176 15 mg, or insulin glargine. LY3298176 will be administered QW as SC injection in patients with T2D who are already treated with a stable dose of at least 1 and no more than 3 oral antihyperglycemic medications: metformin, sodium-glucose co-transporter-2 inhibitors, or sulfonylureas.

Table GPGM.3 shows the randomized treatments for the entire treatment period.

The starting dose of LY3298176 will be 2.5 mg QW for 4 weeks, followed by an increase to 5 mg QW, for the duration of the study low-dose arm. For the 10-mg arm, the starting dose of trizepatide will be 2.5 mg QW for 4 weeks, then the dose will be increased by 2.5 mg every 4 weeks (2.5 to 5 to 7.5 to 10 mg) until the 10-mg dose is reached and maintained for the duration of the study. For the 15-mg arm, the starting dose of LY3298176 will be 2.5 mg QW for 4 weeks, then the dose will be increased by 2.5 mg every 4 weeks (2.5 to 5 to 7.5 to 10 to 12.5 to 15 mg) until the 15-mg dose is reached and maintained for the duration of the study.

The starting dose of insulin glargine will be 10 IU/day at bedtime, titrated to a FBG <100 mg/dL, following a treat-to-target algorithm (Riddle et al. 2003). Patients will titrate the insulin glargine dose in a weekly manner and will make the dose decision with the investigator for the first 8 weeks (phone or clinic visit). For further dose titration, from Week 8 to Week 16, patients will have a phone or clinic visit every other week.

Table GPGM.3. LY3298176 Treatment Regimens

Treatment Group						Treatment Period Interval	
	Weeks 0 to 3	Weeks 4 to 7	Weeks 8 to 11	Weeks 12 to 15	Weeks 16 to 19	Weeks 20 to 104	
15 mg LY3298176	2.5 mg	5 mg	7.5 mg	10 mg	12.5 mg	15 mg	→
10 mg LY3298176	2.5 mg	5 mg	7.5 mg	10 mg →			
5 mg LY3298176	2.5 mg	5 mg →					

Note: All doses will be administered QW using a single-dose prefilled syringe.

The investigator or his or her designee is responsible for the following:

- explaining the correct use of the investigational agent(s) to the patient
- verifying that instructions are followed properly
- maintaining accurate records of investigational product dispensing and collection as well as records of interruptions in study drug administration

- patient should be instructed to discard all used syringes for LY3298176 or pens for insulin glargine in a closeable, puncture-resistant container and dispose according to local regulations

7.1.1. Packaging and Labeling

The sponsor will provide LY3298176 in prefilled syringes and insulin glargine in prefilled pens. These will be dispensed via an interactive web-response system (IWRS). Prefilled syringes and prefilled pens will be packaged in cartons to be dispensed. Clinical trial materials will be labeled according to the country's regulatory requirements.

7.1.2. Medical Devices

The combination products provided for use in the study are LY3298176 investigational prefilled syringe and a marketed insulin glargine prefilled pen.

7.2. Method of Treatment Assignment

Patients who meet all criteria for enrollment will be randomized to 1 of the study treatment arms at Visit 3. Assignment to treatment arms will be determined by a computer-generated random sequence using an IWRS. Patients will be randomized in a 1:1:1:3 ratio to receive 5 mg LY3298176, 10 mg LY3298176, 15 mg LY3298176, or insulin glargine. The randomization will be stratified by country, baseline HbA1c concentration ($\leq 8.5\%$, $>8.5\%$ [≤ 69 , >69 mmol/mol]), and baseline SGLT-2i use (Yes or No).

7.2.1. Selection and Timing of Doses

7.2.1.1. LY3298176

Assignment to LY3298176 (3 doses) or insulin glargine will occur at randomization.

There are no restrictions on the time of day each weekly dose of LY3298176 is given, but it is advisable to administer the SC injections on the same day and same time each week. The actual date and time of all dose administrations will be recorded by the patient. If a dose of LY3298176 is missed, the patient should take it as soon as possible unless it is within 72 hours of the next dose, in which case, that dose should be skipped and the next dose should be taken at the appropriate time.

7.2.1.2. Insulin Glargine

Dosing for patients randomized to insulin glargine will start at 10 units once daily. Patients should administer their daily doses at the time of day agreed upon between the patient and the investigator, typically before bedtime. Patients assigned to the insulin glargine treatment arm will be instructed to adjust insulin glargine doses to a target FBG of <100 mg/dL (5.6 mmol/L) based on the median value of the last 3 self-monitored fasting blood glucose (SMBG) values according to the schedule below (Riddle et al. 2003). Insulin glargine dose adjustments should occur once in a week. After Week 8, patients will continue to adjust insulin glargine per the titration algorithm; the insulin glargine dose will be also reviewed and revised, as needed, at subsequent office visits. There will be no central oversight of insulin glargine titration. Add-on

glycemic rescue therapy should be initiated for patients who met prespecified criteria for severe, persistent hyperglycemia, and further titration of glargine cannot control the condition (see [Table GPGM.4](#)).

Table GPGM.4. Titration of Insulin Glargine

Median Fasting Blood Glucose ^a		Adjustment of Insulin Glargine
mg/dL	mmol/L	
≤70	≤3.9	Decrease by 2 to 4 units ^{b,c}
71 to 99	4.0 to 5.5	No adjustment
100 to 119	5.6 to 6.6	Increase by 2 units
120 to 139	6.7 to 7.7	Increase by 4 units
140 to 179	7.8 to 9.9	Increase by 6 units
≥180	≥10.0	Increase by 8 units

Abbreviation: SMBG = self-monitored blood glucose.

^a Based on the last 3 self-monitored fasting blood glucose (SMBG) values.

^b Dose should also be decreased by 2 to 4 units in the following situations:

- If multiple episodes of nonsevere hypoglycemia were recorded during the assessment period at any time during the day; and/or
- If at least 1 episode that met the criteria for severe hypoglycemia (events requiring assistance to administer therapy) or was associated with self-monitored blood glucose (SMBG) value <54 mg/dL (<3.0 mmol/L) was recorded during the assessment period.

^c If only 1 hypoglycemic episode with SMBG value ≥54 mg/dL (≥3.0 mmol/L) and ≤70 mg/dL (≤3.9 mmol/L) was recorded, insulin dose should not be changed.

Source: Riddle et al. 2003.

